### Exclusion Criteria

A potential subject who meets any of the following exclusion criteria is ineligible to participate in the study.

1. Pathologic evidence of extranodal extension.
2. Pathologic evidence of a final positive margin (R1 resection) or gross residual disease (R2 resection).
3. HPV-positive squamous cell carcinoma.
4. Prior invasive malignancy within the past 3 years (except for non-melanomatous skin cancer, and early stage treated prostate cancer).
5. Life expectancy less than 12 months.

6. Performance status Zubrod  $\geq 3$ .
7. Patients with prior radiation therapy to the head and neck. Note: Prior external beam radiotherapy is excluded, but Iodine 131 is allowed.
8. Prior systemic therapy, including cytotoxic chemotherapy, biologic/targeted therapy, or immune therapy for the study cancer.
9. Body weight  $\leq 30$  kg.
10. Any of the following severe laboratory abnormalities within 14 days of registration, unless corrected prior to it: Sodium  $< 130$  mmol/L or  $> 155$  mmol/L; Potassium  $< 3.5$  mmol/L or  $> 6$  mmol/L; Fasting glucose  $< 40$  mg/dl or  $> 400$  mg/dl; Serum calcium (ionized or adjusted for albumin)  $< 7$  mg/dl or  $> 12.5$  mg/dl; Magnesium  $< 0.9$  mg/dl or  $> 3$  mg/dl.
11. Unstable angina and/or congestive heart failure requiring hospitalization within 3 months prior to Step 1 registration.
12. Transmural myocardial infarction within 3 months prior to Step 1 registration.
13. Medical or psychiatric illness which would compromise the patient's ability to tolerate treatment or limit compliance with study requirements.
14. Pregnancy or women of childbearing potential and men who are sexually active and not willing/able to use medically acceptable forms of contraception during treatment and for 6 months after radiation, this exclusion is necessary because the treatment involved in this study may be significantly teratogenic. Women who are breastfeeding are also excluded.

*"I have reviewed all inclusion and exclusion criteria and confirm the subject is eligible."*

---

**(Date)**

#### **4.7 Discontinuation of Study Treatment, Withdrawal, and Compliance**

Discontinuation from the study treatment does not mean discontinuation from the study. Subject will be considered in follow-up, study procedures should still be completed as indicated by the study protocol, and AEs/SAEs will continue to be reported according to this protocol.

In the absence of treatment delays due to adverse events, study treatment/intervention may continue until:

- Disease progression.
- General or specific changes in the subject's condition renders the subject unacceptable for further treatment in the investigator's judgment.
- Inter-current illness that prevents further treatment administration.
- Subject decides to withdraw from the study.
- The subject has significant noncompliance with the protocol (see below).
- Unacceptable adverse event(s) and/or dose level reduction beyond requirements as detailed in this protocol.
- Study stopping rules are met.

Subjects who sign the informed consent form, enroll and receive the study intervention, but subsequently withdraw, or are withdrawn or discontinued from the study will not be replaced.

#### **Consent Withdrawal**

A subject may decide to withdraw from the study at any time. MCW IRB of record's SOPs regarding consent withdrawal will be followed. If a subject intends on withdrawing consent, staff should confirm which of the following options the subject chooses and document the discussion:

- Full consent withdrawal, with no study follow-up.
- Selective consent withdrawal from interventional portion of the study but agree to continued follow-up of associated clinical outcome information.

#### **Investigator-initiated Withdrawal**

The investigator will withdraw a subject whenever continued participation is no longer in the subject's best interests. Reasons for withdrawing a subject include, but are not limited to, disease progression, the occurrence of an adverse event or a concurrent illness, a subject's request to end participation, a subject's noncompliance or simply significant uncertainty on the part of the investigator that continued participation is prudent. The reason for study withdrawal and the date the subject was removed from the study must be documented.

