## STUDY SCHEMA

## STUDY CALENDAR

Study Assessment	Screening	Pre-Intervention*	Intervention**					Follow-up (until 12-months post RT)***			
Procedures	Day -30 to Enrollment	Simulation & Evaluations	RT 1	RT 2-4	RT 5	RT 6-completion	Final Fraction of RT (+/- 48 hours)	2, 4, and 6 wk Post-RT Follow-Up (+/- 7 days)	3 mo Post-RT Follow-Up (+/- 14 days)	6 mo Post-RT Follow-Up (+/- 14 days)	9 and 12 mo Post-RT Follow-up (+/- 14 days)
Informed Consent	X										
Physical Exam (Radiation Oncologist) 	X		X (One visit no later than 24 hours after fraction 5)			X (One visit to be completed no later than 24 hours after final RT fraction)		X	X	X	X
Physical Exam (Surgical Oncologist) 	X								X	X	X
Performance Status	X		X (One visit no later than 24 hours after fraction 5)			X (One visit to be completed no later than 24 hours after final RT fraction)		X	X	X	X
Medical History	X										
Concomitant Medications	X		X (One visit no later than 24 hours after fraction 5)			X (One visit to be completed no later than 24 hours after final RT fraction)		X	X	X	X
AE Assessment	Recorded until completion of the 12-month follow-up period										
Basic Metabolic Panel 	X										
Magnesium (Mg) 	X										
Fasting glucose 	X										
Pregnancy Test 	X										
CT/MR Simulation		X									
Radiotherapy 			X	X	X	X	X				
Radiation Planning		X									
SLP Evaluation		X						X	X	X	X
VFSS Study 		X							X	X	
DIGEST Grade		X							X	X	
FACT- HN Survey		X					X	X	X	X	X
MDADI Survey		X					X	X	X	X	X

Study Assessment	Screening	Pre-Intervention*	Intervention**					Follow-up (until 12-months post RT)***			
Procedures	Day -30 to Enrollment	Simulation & Evaluations	RT 1	RT 2-4	RT 5	RT 6-completion	Final Fraction of RT (+/- 48 hours)	2, 4, and 6 wk Post-RT Follow-Up (+/- 7 days)	3 mo Post-RT Follow-Up (+/- 14 days)	6 mo Post-RT Follow-Up (+/- 14 days)	9 and 12 mo Post-RT Follow-up (+/- 14 days)
Total opioid intake		X					X	X	X	X	X
Visual analog pain scale		X					X	X	X	X	X
Neck CT or MRI and Chest CT or PET/CT of chest 	X								X		

\* Should be completed before starting radiation treatment

\*\* Scheduled as per institutional guidelines and study protocol

\*\*\* If a subject has disease progression/relapse or subject withdrawal, then they will be followed as per follow-up requirements.

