To assess efficacy of the HART-HN regimen assessment of locoregional control and overall survival will be made by the treating radiation oncologist or surgeon at each follow-up, by clinical examination of the head and neck as per the standard of care. Standard post-treatment imaging including a neck CT (with or without contrast) or MRI and a chest CT (with or without contrast) or PET/CT (with or without contrast) will be obtained at 3 months post-treatment (+/- 2 weeks), as per standard of care. Additional surveillance imaging in the follow-up setting has not shown any benefit in 3-year disease-free survival as compared to ongoing clinical surveillance. Therefore, patients will be clinically followed for disease control until locoregional progression, completion of the 12-month follow-up period, patient refusal, or death.

In order to understand the acute and long-term toxicities of the HART-HN regimen patients will be followed clinically by the treating radiation oncologist, undergo routine FACT-HN and MDADI surveys, and undergo scheduled SLP visits including VFSS and DIGEST grading as detailed in the prior section. For the purposes of this study, acute toxicity will be deemed any toxicity that occurs within 90 days of completion of radiation therapy, and late toxicity will be deemed any toxicity that occurs more than 90 days after completion of radiation therapy. During each weekly treatment review and each post-treatment follow-up, the treating physician will record a pain score (scale 1-10) and use the Common Terminology Criteria for Adverse Events Version 5.0 (CTCAE) to record toxicity scores for dysphagia, oral mucositis, dehydration and weight loss. The treating physician will also record tracheostomy tube dependence and feeding tube dependence at each visit.

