### 4.1 Subject Status

Subject statuses throughout the trial are defined as follows:

- Prescreening: preconsent (subject considering trial or study staff considering patient for the trial per institutional recruitment methods).
- Screening: period after consent, but prior to eligibility confirmation.
- Consented: consented, prior to eligibility confirmation.
- Eligible: the local investigator confirms all eligibly criteria apply.
- On study/enrolled: date eligibility is confirmed.
- On arm: date of enrollment.
- On treatment: first day treatment was given to the last day treatment was given.
- Off treatment: the last day treatment was given.
- On follow-up: from last day of treatment to the end of follow-up period.
- Off study: follow-up period completed, with no additional data gathered.
- Withdrawn: subject fully withdraws consent (i.e., refuses ALL follow-up, even survival) or is taken off study by the local principal investigator.

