## **6.2 Collection and Reporting Requirements for Adverse Events and Serious Adverse Events**

### **6.2.1 Collection of Adverse Events**

All AEs (including SAEs) must be recorded in OnCore® and REDCap (as applicable) and/or an Adverse event log. All AEs required to be collected must be graded according to the CTCAE v5. When possible, signs and symptoms indicating a common underlying pathology should be noted as one comprehensive event. Investigator's or Treating physician's assessment of AE attributions must also be documented.

AEs will be collected from the time the subject signs the consent form through completion of the entire 12-month follow-up period. After this period, investigators should only report SAEs that are attributed to prior study treatment. AEs will be tracked and followed until resolution, subject withdraws consent, or is lost to follow-up (including subjects who discontinue early). All adverse events collected per the protocol will be followed with appropriate medical management until they are resolved, if they are related to the study treatment, or until the investigator deems the event to be chronic.

Please see section 6.2.2 and table 2 to identify the adverse events that need to be reported.

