#### **Patient Discontinuation from Study**

Patients have the right to voluntarily withdraw from the study at any time for any reason. In addition, the investigator has the right to withdraw a patient from the study at any time. Reasons for patient discontinuation from the study may include, but are not limited to, the following:

- Patient withdrawal of consent
- Study termination
- Adverse event
- Loss to follow-up
- Patient non-compliance, defined as failure to comply with protocol requirements as determined by the investigator or Sponsor

Every effort should be made to obtain a reason for patient discontinuation from the study. The primary reason for discontinuation from the study should be documented on the appropriate eCRF. If a patient requests to be withdrawn from the study, this request must be documented in the source documents and signed by the investigator. Patients who withdraw from the study will not be replaced.

If a patient withdraws from the study, the study staff may use a public information source (e.g., county records) to obtain information about survival status.

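### Investigator removal from the study for an adverse event or progression may cut off DLT and survival data, and the protocol contradicts itself on whether follow-up continues

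*Combined protocol and SAP*

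**What the plan says.** Three places treat the investigator's decision as removal from the study.

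- Section 4.7, Investigator-initiated Withdrawal: "Reasons for withdrawing a subject include, but are not limited to, disease progression, the occurrence of an adverse event or a concurrent illness". The same paragraph asks for the date of removal from the study, not from treatment.
- Section 4.1 defines the status Withdrawn as "subject fully withdraws consent (i.e., refuses ALL follow-up, even survival) or is taken off study by the local principal investigator". One status covers both cases.
- Section 7.4, Patient Discontinuation from Study: "the investigator has the right to withdraw a patient from the study at any time". The reasons listed there include an adverse event.

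Other places keep the patient under observation.

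- Study calendar, third footnote: "If a subject has disease progression/relapse or subject withdrawal, then they will be followed as per follow-up requirements".
- Section 6.2.1 collects adverse events to the end of the 12-month follow-up and adds: "AEs will be tracked and followed until resolution, subject withdraws consent, or is lost to follow-up (including subjects who discontinue early".
- Section 4.7, opening: "Discontinuation from the study treatment does not mean discontinuation from the study".
- Section 7.4 allows staff to look up survival in public records after a withdrawal, but as an option.

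For the analysis, Section 7.2.1 keeps everyone who starts radiation evaluable for the primary endpoint. Sections 4.7 and 7.4 rule out replacement. The only DLT censoring rule, in Section 7.1, concerns death from progression without radiation toxicity.

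**The concern.** Section 1.2 says every regimen finishes in two weeks or less. Section 7.1 counts DLTs to 12 months after radiation. For most of that window there is no study treatment left to stop, so taking a patient off study can change only what is recorded.

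The permitted reasons are also related to the outcomes. Many DLTs are Grade 4 or higher late events (Section 7.2.1), such as tissue necrosis needing reconstruction or laryngeal edema needing a tracheostomy. A lower-grade adverse event can plausibly come first. Progression often comes before death. If patients leave observation for these reasons, the censoring is informative. The DLT rate can then look lower than it is, and Kaplan-Meier survival can look higher.

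With 18 patients, one or two missed events matter, both for the comparison with the 33% limit and for the efficacy signal that Section 2 wants as a basis for later trials.

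**Working it through.** **1. The passages side by side**

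| Question | Sections 4.1, 4.7 (investigator-initiated) and 7.4 | Calendar footnote, Section 6.2.1 |
|---|---|---|
| May an adverse event end study participation? | Yes (4.7, 7.4) | Adverse events are followed until resolution, consent withdrawal or loss to follow-up; investigator removal is not an end point |
| May progression end it? | Yes (4.7) | Follow-up continues |
| What is collected after removal? | Same status as refusal of all follow-up; survival lookup optional | Follow-up as required by the protocol |

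The Consent Withdrawal part of Section 4.7 offers a choice that keeps outcome follow-up. The investigator-initiated part offers none. No sentence ranks the two columns.

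**2. How much of the window is affected**

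For the longest regimen, taken as two weeks, followed by 52 weeks: 52/(52 + 2) = 96% of the time on study falls after radiation.

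**3. Size, for assumed shares of missed events**

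The plan has no figure of its own to reproduce here: none of the five simulation assumptions in Section 7.3 concerns withdrawal. Inputs:

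- DLT limit 33% over 12 months (Section 7.1).
- Constant DLT and death hazards, and one-year survival of 75.4% (Section 7.3).
- A true DLT rate p of 40%, assumed as an example just above the limit.
- A share f of events missed because the patient is removed first, assumed at 10%, 25% and 50%.

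If removal hides a constant share f of events, and removed patients are censored when they leave, the observed hazard is (1 − f) times the true one:

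- apparent DLT rate = 1 − (1 − p)^(1 − f)
- apparent survival = 0.754^(1 − f)

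| f | DLT rate, true 40% | Survival, true 75.4% |
|---|---|---|
| 0 | 40.0% | 75.4% |
| 10% | 1 − 0.60^0.90 = 36.9% | 0.754^0.90 = 77.6% |
| 25% | 1 − 0.60^0.75 = 31.8% | 0.754^0.75 = 80.9% |
| 50% | 1 − 0.60^0.50 = 22.5% | 0.754^0.50 = 86.8% |

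The 40% rate drops to the 33% limit when 1 − f = ln 0.67 / ln 0.60 = 0.784, that is, when about 22% of DLTs are missed.

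**4. The same in patients**

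Take six patients at a level (assumed), two of whom would have a DLT: 2/6 = 33.3%. Suppose one of the two is removed at month 3 before the DLT, and the rest are fully observed. Counted as DLT-free for the whole window, the rate is 1/6 = 16.7%. Weighted by the quarter of the window observed, it is 1/(5 + 3/12) = 19.0%. The documents do not say which treatment, if either, applies.

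Expected deaths within a year are 18 × (1 − 0.754) = 4.4, so one lost death is nearly a quarter of them (1/4.4 = 23%).

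**The case against.** The strongest reply is that the protocol already protects the data. Section 6.2.1 names early discontinuers and does not list investigator removal as an end to adverse event follow-up. A worsening Grade 3 event is exactly what it would go on tracking. The calendar footnote says the same for progression and withdrawal. A reader might infer from Sections 4.1 and 4.7 that removal definitely ends DLT and survival follow-up. The documents do not establish that; they conflict.

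Further points stand:

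- Removal is a best-interests judgment, and nothing suggests it would be frequent.
- A DLT already recorded still counts. Bias in the DLT rate needs removal before the DLT and for a reason related to it.
- Removal for progression should have little effect on the DLT result when DLT risk is unrelated to progression. Its main effect is on overall survival, a secondary endpoint. A locoregional recurrence that prompts removal is already an event for locoregional control.
- The opening of Section 4.7 concerns stopping treatment, which is a different act from leaving the study. It does not by itself contradict the investigator-initiated paragraph.
- Section 3.1 might be read as ending all follow-up at progression. It does not: "patients will be clinically followed for disease control until locoregional progression" limits that cut-off to disease control.

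What does not stand is that this settles the matter. Section 4.1 still puts the removed patient with those who refuse everything, and staff must choose which passage to follow. The public-record lookup is optional and can find deaths but not DLTs.

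**Conclusion.** The protocol permits removal from the study for reasons that can predict the outcomes, and it gives conflicting instructions on what is collected afterwards. That is a real and avoidable route to informative censoring, and it should be closed.

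It is a conditional risk. A reader might infer that the DLT rate is biased down at every level, or that a removed patient stays in the TITE-CRM as DLT-free with a frozen partial weight. Neither follows: the first depends on which passage is applied and how often, and the second appears nowhere in the documents.

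The figures above rest on an assumed true DLT rate, assumed shares of missed events, constant hazards and censoring at removal. They show that a level at 40% could read as under 33% once roughly a fifth or more of its DLTs are missed, and that survival could read between 2 and 11 points too high for shares from 10% to 50% (77.6 − 75.4 = 2.2; 86.8 − 75.4 = 11.4). I put no figure on the chance of selecting the wrong level, because the documents give no skeleton or prior for the TITE-CRM.

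**What to change.** 1. Reconcile Sections 4.1, 4.7 (Investigator-initiated Withdrawal) and 7.4 with the calendar footnote, Section 6.2.1 and the opening of 4.7. State that every patient who starts radiation stays in DLT, adverse event and survival follow-up to 12 months, whatever adverse event, progression or later therapy occurs. Only the patient's refusal of follow-up, or loss to follow-up as defined in Section 4.8, ends outcome collection.
2. In Section 4.1, give investigator removal and full consent withdrawal separate statuses.
3. In Section 7.1, state how a patient without complete follow-up is weighted in the TITE-CRM, including one who withdraws or is lost.

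Section 3.1 needs no change. The amendment concerns data collection only and alters no rule for stopping treatment. It costs protocol wording and uses visits already in the calendar.

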#### **4.8 Lost to Follow-Up**

The following actions must be taken if a participant fails to return to the clinic for a required study visit and/or is unable to be reached for follow-up:

- The investigator or designee must make every effort to regain contact and/or reschedule a missed visit with the participant.
- A participant is deemed lost to follow-up if his/her status cannot be obtained after *all* of the following occurs at two consecutive scheduled protocol calendar timepoints:
  - Three telephone calls (at least one day apart) from the study team are unanswered,

**AND**

- A letter (Appendix 2) to the participant's last known mailing address goes unanswered, **AND**
- These contact attempts must be documented in the participant's medical record or study file.
- Update OnCore®/REDCap (Follow-Up tab and eCRF) when a participant is officially considered lost to follow-up.
- If a subject is considered lost to follow-up, but subsequently contacts the study team, the subject should be considered in follow-up again.

#### **4.9 Accrual Suspension and Closure**

The MCW PI facilitates the suspension and closing of accrual in the following manner:

- OnCore® and REDCAP track accrual throughout the study.
- If the study must be suspended, OnCore® and REDCap are updated to a 'suspended' status.
- When the accrual number is reached, OnCore® and REDCap notifies staff of study closure.

#### **4.10 End of Study Definition**

A participant is considered to have completed the study if he or she completed all phases of the study, including the last visit or the last scheduled procedure shown in the calendar of events or has been discontinued.

#### **4.11 Study Discontinuation and Closure**

This study may be temporarily suspended or prematurely terminated if there is sufficient reasonable cause (as determined by the MCW study PI, DSMC, sponsor, and/or IRB). Written notification, documenting the reason for study suspension or termination, will be provided by the suspending or terminating party to study participants, investigator, funding agency, the Investigational New Drug (IND) sponsor and regulatory authorities. If the study is prematurely terminated or suspended, the MCW principal investigator (PI) will promptly inform the MCW Institutional Review Board (IRB), and the sponsor and will provide the reason(s) for the termination or suspension. Study participants will be contacted, as applicable, and be informed of changes.

### **5 TREATMENT PLAN**

#### **5.1 Radiation Therapy**

Radiation therapy will be delivered using intensity modulated radiation therapy with daily cone-beam CT.

##### **5.1.1 Simulation, Localization and Treatment Planning Requirements**

Patients must be immobilized using a thermoplastic head mask extending to include neck and shoulder immobilization.

Treatment planning CT and/or images will be required for target volume delineation including gross tumor volume (GTVs), clinical target volumes (CTVs) and planning target volumes (PTVs). CT will be used for dose calculation. All tissues to be irradiated should be included in the CT scan. CT slice thickness should be 2 mm or less. MR simulation is optional.

Daily Cone-Beam CT is required.

